25. **Adverse Event (AE) Assessments:** AEs should be documented and recorded at each visit using the National Cancer Institute Common Terminology Criteria for Adverse Events (NCI CTCAE) version 4.03. The severity of cytokine release syndrome (CRS) will be assessed according to the grading described by Lee et al. (2014 and 2019,^{2,3} See [Appendix 5](#)) instead of CTCAE. In addition, ASTCT consensus grading of CRS and ICANS³ will be captured separately from the AE assessments (See [Appendix 5](#)). The time period for actively eliciting and collecting AEs and SAEs (“active collection period”) for each patient begins from the time the patient provides informed consent through and including a minimum of 90 calendar days after the last investigational product administration. If the patient begins a new anticancer therapy, the period for recording non-serious AEs on the case report form (CRF) ends at the time the new treatment is started. However, any SAEs occurring during the active collection period must still be reported to Pfizer Safety and recorded on the CRF, irrespective of any intervening treatment.
26. **Concomitant Treatments:** all concomitant medications and Nondrug Supportive Interventions should be recorded on the CRF.
27. **Genetic Analysis:** Bone marrow aspirates taken on C1D1 will be evaluated at local lab for t(4;14)(p16;q32), t(14;16)(q32;q23), 17p13 deletions, t(11;14)(q13;q32), chromosome 13 deletion, ploidy category, and chromosome 1 abnormalities. If some of these cytogenetic assessments cannot be done, site should provide patient's most recent cytogenetic testing results and enter into Ecrf. Sample may be taken up to 7 days before the start of study treatment.
28. **BCMA+ expression on multiple myeloma cells in bone marrow:** Expression of BCMA will be evaluated on fresh bone marrow aspirates (by flow cytometry) and biopsies (by IHC). Expression of additional markers including CD138 will also be evaluated. Additional analyses may be performed on bone marrow biopsies, including immunophenotyping of infiltrating immune cells and exploratory molecular analyses. If the sample collection day coincides with days whereby investigational product is to be administered, samples will be collected prior to investigational product administration. Sample for Cycle 1 Day 1 (C1D1) may be taken up to 7 days before study treatment; samples at 1 and 3 months after C1D1 will be collected ±7 days; samples at 9 months after C1D1 will be collected ±14 days.
29. **Soluble BCMA:** See [Schedule of Pharmacokinetic, Soluble Factor and Cytokine Activities C](#). Soluble BCMA will be measured in plasma by mass spectrometry.
30. **TBNK and Immunophenotyping:** enumeration and phenotypes of T-cell subsets by multiparameter flow cytometry. If sample collection day coincides with days whereby investigational product is to be administered, samples will be collected prior to investigational product administration. Bone marrow sample for Cycle 1 Day 1 (C1D1) may be taken up to 7 days before study treatment; samples at 1 month or 3 months after C1D1 will be collected ±7 days.

PF-06863135

C1071001

Final Protocol Amendment 9, 28 March 2023

| Schedule of Activities C Visit Identifier | Screening ¹ Days prior to enrollment | Treatment Period | | | | | | | | | | | | | | | | 1 month Follow-up ³⁴ | | | Survival Follow-up ³⁶ | |
|--|--|--------------------------------|---|---|---|---------|----|----|----|-----------------|----|----|----|-------------------|----|----|----|------------------------------------|------|------|-------------------------------------|-----|
| | | Cycle 1 (1 Cycle = 4 weeks) | | | | Cycle 2 | | | | Cycle 3 onwards | | | | EOT ³⁵ | | | | | | | | |
| Study Day | -28 to -1 | -14 to -1 | 1 | 2 | 3 | 4* | 8 | 15 | 22 | 1 | 4* | 8 | 15 | 22 | 1 | 8 | 15 | 22 | 28 d | 90 d | 120 d | |
| Visit Window (days) | | | | | | | ±1 | ±1 | ±1 | ±1 | ±1 | ±1 | ±2 | ±2 | ±2 | ±2 | ±2 | ±2 | +7 | +7 | +7 | ±14 |

When bone marrow aspirate samples are taken for disease response evaluation, samples for TBNK and immunophenotyping will also be acquired. In the event of SC dose route, omit C1D2 collection.

31. **Gene expression ribonucleic acid (RNA) profile:** gene expression associated with activation state and anti-tumor activity will be measured by RNA sequencing in bone marrow. If sample collection day coincides with days whereby investigational product is to be administered, samples will be collected prior to investigational product administration. Bone marrow sample for Cycle 1 Day 1 (C1D1) may be taken up to 7 days before study treatment; samples at 1 month or 3 months after C1D1 will be collected ±7 days; samples at 9 months after C1D1 will be collected ±14 days. When bone marrow aspirate samples are taken for disease response evaluation, samples for gene expression analysis will also be acquired. In the event of SC dose route, omit C1D2 collection.
32. **T-cell receptor (TCR) sequencing:** clonal expansion, contraction and diversity and its association with activity and durability will be assessed by deoxyribonucleic acid (DNA) sequencing of TCR in bone marrow. If sample collection day coincides with days whereby investigational product is to be administered, samples will be collected prior to investigational product administration. Bone marrow sample for Cycle 1 Day 1 (C1D1) may be taken up to 7 days before study treatment; samples at 1 month or 3 months after C1D1 will be evaluated ±7 days; samples at 9 months after C1D1 will be collected ±14 days. When bone marrow aspirate samples are taken for disease response collected, samples for TCR sequencing will also be acquired.
33. **Genomic banked biospecimens Prep D1:** If not collected on C1D1, collect at the next available time point when biospecimens are being collected in conjunction with a patient visit.
34. **One month follow-up:** At least 28 calendar days, and no more than 35 calendar days, after discontinuation of treatment, patients will return to undergo review of concomitant treatments, vital signs, and assessment for resolution of any treatment-related toxicity. Patients continuing to experience toxicity at this point following discontinuation of treatment will continue to be followed at least every 4 weeks until resolution or determination, in the clinical judgment of the investigator, that no further improvement is expected. If the patient completes the follow-up visit prior to completion of the 60 day long term dose limiting toxicity (DLT) observation period, a follow up phone call will be completed on at least Day 60, and no more than Day 65.
35. **End of Treatment (EOT) Visit:** Obtain these assessments if not completed in the last week (last 4 weeks for disease assessments).
36. **Survival follow up:** Following discontinuation of study treatment (unless patients are lost to follow up, consent is withdrawn, or study is discontinued by the sponsor), survival status will be collected by telephone every 3 months until death, or up to approximately 30 months after last patient first dose, whichever comes first. Subsequent anti-cancer therapies and relevant transplant information will also be collected. Any SOC disease assessments obtained between EOT and subsequent anti-cancer therapy will be collected.
37. **Local Site Injection Tolerability Assessment (SC Administration Cohort Only):** Assessment of injection site should be conducted at 1 to 4 hours following treatment administration on Day 1, 8 and 15 for the first cycle. If injection site pain or injection site reaction (ISR) characteristics continue to persist after the first cycle, local site injection tolerability assessments should continue until the symptoms resolve.

PF-06863135

C1071001

Final Protocol Amendment 9, 28 March 2023

| Schedule of Activities C Visit Identifier | Screening ¹ Days prior to enrollment | Treatment Period | | | | | | | | | | | | | | | | 1 month Follow-up ³⁴ | Survival Follow-up ³⁶ | | |
|--|--|--------------------------------|---|---|---|---------|----|----|----|-----------------|----|----|----|-------------------|----|----|----|------------------------------------|-------------------------------------|------|-------|
| | | Cycle 1 (1 Cycle = 4 weeks) | | | | Cycle 2 | | | | Cycle 3 onwards | | | | EOT ³⁵ | | | | | | | |
| Study Day | -28 to -1 | -14 to -1 | 1 | 2 | 3 | 4* | 8 | 15 | 22 | 1 | 4* | 8 | 15 | 22 | 1 | 8 | 15 | 22 | 28 d | 90 d | 120 d |
| Visit Window (days) | | | | | | | ±1 | ±1 | ±1 | ±1 | ±1 | ±1 | ±2 | ±2 | ±2 | ±2 | ±2 | ±7 | ±7 | ±7 | ±14 |

38. **Treatment with lenalidomide:** A dose of 15 mg of lenalidomide will be administered orally on days 1-21 over a 28 day cycle. For subsequent cycles, dosing will be every 4 weeks. Day 1 safety laboratory test results need to be reviewed by the investigator prior to dosing at the beginning of each cycle for dosing confirmation.

39. **Treatment with pomalidomide:** A dose of 4 mg of pomalidomide will be administered orally on Days 1-21 over a 28 day cycle. Day 1 safety laboratory test results need to be reviewed by the investigator prior to dosing at the beginning of each cycle for dosing confirmation.

PF-06863135

C1071001

Final Protocol Amendment 9, 28 March 2023

SCHEDULE OF PHARMACOKINETIC, SOLUBLE FACTOR AND CYTOKINE ACTIVITIES C: PARTS 1 SC Q2W, 1C AND 1D (DOSE ESCALATION COMBINATION) AND 2A, 2C AND 2D (DOSE EXPANSION COHORTS) WITHOUT PRIMING DOSE

The schedule of pharmacokinetic, soluble factor and cytokine activities table provides an overview of the protocol visits and procedures. This schedule of activities (both gray and white columns) is applicable to Parts 1C, 1D, 2A, 2C and 2D as well as Part 1 SC Q2W dosing without a priming dose. Please refer to [Schedule of Activities B](#) for if priming dose and maintenance is selected.

Grayed out columns should only be performed if Q1W dosing of PF-06863135 is selected but not for Q2W dosing.

The investigator may schedule visits (unplanned visits) in addition to those listed in the schedule of activities table in order to conduct evaluations or assessments required to protect the well-being of the patient. See [Appendix 10](#) for alternative measure guidelines due to COVID-19.

| Visit Identifier | Up to 7 days prior to C1D1 | Treatment Period | | | | | | | | | | | | | | | | | | | | | | EOT | |
|--|----------------------------|------------------|---|---------|-------|--------|---------|---|---|---------|---|---------|---|----|---|---|---------|--------|-----|-----------------|-----|---|--|-----|---|
| | | Cycle 1 | | | | | | | | | | Cycle 2 | | | | | | | | Cycle 3 onwards | | | | | |
| Study Day | | D1 | | | D2 | D4 | D8 | | | D15 | | D22 | | D1 | | | D4 | D8 | D15 | | D22 | | D1 | | |
| | | 0 | 2 | 4 | 8 | 24 | 72 | 0 | 2 | 4 | 0 | 2 | 0 | 2 | 0 | 2 | 4 | 72 | 0 | 2 | 0 | 2 | 0 | 2 | |
| Visit window | | | | ±0.5 hr | ±1 hr | ±3 hrs | ±24 hrs | | | ±0.5 hr | | | | | | | ±0.5 hr | ±24 hr | | | | | | | |
| Cytokine evaluation in serum ¹ | X | X | X | X | X | X | X | X | X | X | X | X | X | X | X | X | X | X | X | X | X | X | 3 (±7 days) and 9 months (±14 days) after C1D1 | | |
| Samples for PF-06863135 blood level (Parts 1 SC, 1C, and 1D only) ² | | X | | | X | X | X | X | | | X | | X | | X | | X | X | | X | X | X | X ² | | X |

PF-06863135

C1071001

Final Protocol Amendment 9, 28 March 2023

090177e19d0be7ca\Approved\Approved On: 29-Mar-2023 19:51 (GMT)

| Visit Identifier | Up to 7 days prior to C1D1 | Treatment Period | | | | | | | | | | | | | | | | | | | | EOT | |
|---|-------------------------------------|------------------|---|----|----|----|----|---|-----|---|-----|---------|----|---|----|----|-----|---|-----|-----------------|----|----------------|----------------|
| | | Cycle 1 | | | | | | | | | | Cycle 2 | | | | | | | | Cycle 3 onwards | | | |
| Study Day | Hours Pre/after dosing [†] | D1 | | D2 | D4 | D8 | | | D15 | | D22 | | D1 | | D4 | D8 | D15 | | D22 | | D1 | | |
| | | 0 | 2 | 4 | 8 | 24 | 72 | 0 | 2 | 4 | 0 | 2 | 0 | 2 | 4 | 72 | 0 | 2 | 0 | 2 | 0 | 2 | |
| Samples for PF-06863135 blood level (Parts 2A, 2C, 2D only) ² | | X | | | X | X | X | X | | | X | | X | | | X | X | | X | | X | | X |
| Samples for lenalidomide blood level (Parts 1C and 2C only) ³ | | X | | | | | | X | | | X | | | | | | | | X | | | | |
| Samples for pomalidomide blood level (Parts 1D and 2D only) ³ | | X | | | | | | X | | | X | | | | | | | | X | | | | |
| Blood samples for PF-06863135 ADA and Nab ⁴ | | X | | | | | | | | | X | | | | | | | | X | | | | X ⁴ |
| Soluble BCMA and other factors (Parts 1 SC, 1C, and 1D only) ⁵ | X | X | | | X | X | X | X | | | X | | X | | X | | X | X | | X | | X ⁴ | |
| Soluble BCMA and | X | X | | | X | X | X | | | | X | | X | | X | | | | X | | | X ⁴ | |

PF-06863135

C1071001

Final Protocol Amendment 9, 28 March 2023

| Visit Identifier | Up to 7 days prior to C1D1 | Treatment Period | | | | | | | | | | | | | | | | | | | | EOT | |
|--|----------------------------|------------------|----|----|----|----|---|-----|---|-----|---|---------|---|----|----|---|-----|---|-----|---|----|-----|-----|
| | | Cycle 1 | | | | | | | | | | Cycle 2 | | | | | | | | | | | |
| Study Day | D1 | | D2 | D4 | D8 | | | D15 | | D22 | | D1 | | D4 | D8 | | D15 | | D22 | | D1 | | EOT |
| | 0 | 2 | 4 | 8 | 24 | 72 | 0 | 2 | 4 | 0 | 2 | 0 | 2 | 72 | 0 | 2 | 0 | 2 | 0 | 2 | 0 | 2 | |
| Hours Pre/after dosing [†] | | | | | | | | | | | | | | | | | | | | | | | |
| other factors (Parts 2A, 2C, and 2D only) ⁵ | | | | | | | | | | | | | | | | | | | | | | | |

ADA = Abbreviations: Anti-drug antibodies; BCMA = B-cell maturation antigen; D = Day; EOT = end of treatment; Nab = neutralizing antibodies.

† Sampling times are related to the start of the infusion/injection. All 0 hr samples should be taken prior to dose administration. All efforts will be made to obtain the pharmacokinetic (PK) samples at the exact nominal time relative to dosing. However, samples obtained within the window specified will be acceptable.

 Activities in grayed out columns should only be done for SCPF-0863135 Q1W dosing schedule but skipped for Q2W dosing.

Footnotes for Schedule of Pharmacokinetic, Soluble Factors and Cytokine Activities C

1. **Cytokine evaluation in serum:** See Cytokine Assessments [Section 7.5.4](#) for a full list of cytokine assessments. All samples will be analyzed centrally. All 0 hour samples will be collected prior to investigational product administration on days whereby investigational product is to be administered. If CRS is suspected, an adhoc cytokine sample will be collected(see [Section 7.1.3](#) Laboratory Safety Assessments). Should the site require cytokine information for patient management, the site will have the option of collecting an additional sample for local analysis. If a sample for cytokine panel evaluation is due to be collected on the same day as the day a suspected CRS event occurs, then an ad hoc sample for central analysis is not required/collected. However, an ad hoc sample for local analysis may still be collected for patient management
2. **Blood sample for PF-06863135 blood levels:** Approximately 3 Ml sample of whole blood (to provide approximately 1.5 Ml of serum) will be collected into a 3 Ml vacutainer tube at each time point for PK analysis of PF-06863135. After Cycle 8, pre- and post-dose PK samples will be collected only on every 4th cycle (Cycle 8, Cycle 12, Cycle 16, etc.). An additional PK sample should also be taken if CRS is suspected, and a PK sample is not already scheduled to be taken (eg, Cycle 3 onwards).
3. **Blood sample for lenalidomide and pomalidomide blood levels:** Approximately 3 Ml sample of whole blood (to provide approximately 1.5 Ml of plasma) will be collected into a 3 Ml K₂EDTA vacutainer tube at each time point within 2 hours prior to the administration of lenalidomide and pomalidomide, respectively, for PK analysis of lenalidomide and pomalidomide.

PF-06863135

C1071001

Final Protocol Amendment 9, 28 March 2023

| Visit Identifier | Up to 7 days prior to C1D1 | Treatment Period | | | | | | | | | | | | | | | | | | EOT | |
|-------------------------------------|----------------------------|------------------|----|----|----|----|---|-----|---|-----|---------|----|---|----|----|-----|-----------------|-----|---|-----|---|
| | | Cycle 1 | | | | | | | | | Cycle 2 | | | | | | Cycle 3 onwards | | | | |
| Study Day | D1 | | D2 | D4 | D8 | | | D15 | | D22 | | D1 | | D4 | D8 | D15 | | D22 | | D1 | |
| | 0 | 2 | 4 | 8 | 24 | 72 | 0 | 2 | 4 | 0 | 2 | 0 | 2 | 4 | 72 | 0 | 2 | 0 | 2 | 0 | 2 |
| Hours Pre/after dosing [†] | | | | | | | | | | | | | | | | | | | | | |

4. **Anti PF-06863135 Antibodies (ADA) and Neutralizing Antibodies (Nab):** Two 1 mL pre-dose serum samples (from 5 mL total whole blood) to detect the presence of antibodies to PF-06863135 is to be obtained prior to the start of dose administration. Patients having an unresolved adverse event that is possibly related to anti-PF-06863135 antibodies at the End of Treatment visit will be asked to return to the clinic for ADA and drug concentration blood sampling at approximately 3-month intervals until the adverse event or its sequelae resolve or stabilize at a level acceptable to the investigator and sponsor. After Cycle 4, pre-dose ADA and Nab samples will be collected only on Cycles 6, 8, and every 4th cycle thereafter (Cycle 8, Cycle 12, Cycle 16, etc.).

5. **Soluble BCMA and other factors:** Approximately 3 mL sample of whole blood (to provide approximately 1 mL of plasma) will be collected at each time point for analysis of soluble BCMA and other factors by mass spectrometry. All 0 hour samples will be collected prior to investigational product administration on days whereby investigational product is to be administered. After Cycle 8, pre- and post-dose PK samples will be collected only on every 4th cycle (Cycle 8, Cycle 12, Cycle 16, etc.). An additional soluble BCMA/other factor sample should also be taken if CRS is suspected, and a sample is not already scheduled to be taken (eg, Cycle 3 onwards).

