 - To closely manage acute toxicities, patients in Part 1E will be hospitalized on C1D1. The need for hospitalization as well as its length will be re-assessed for patients enrolled in Part 2E based on safety data from Part 1E after agreement of sponsor and investigators.
 - For Part 1E or Part 2E, patients within these parts may enroll concurrently.
 - It is expected that Part 1E will enroll approximately 9-16 patients.

A modified toxicity probability interval (mTPI) method, targeting a DLT rate of 25% and an acceptable equivalence interval of 20%-30% will be utilized for dose escalation in Part 1. All patients will also be monitored closely for DLTs until the end of Cycle 1. All patients will be monitored for late toxicities following the initial DLT period up to Day 60 from first dose (see [Section 3.2.1](#)). Once a dose level has been declared safe, patients at lower dose levels who have completed the 60 day late toxicity observation period may escalate to the next higher dose level, if criteria outlined in [Section 3.1.4.1 Criteria for Intrapatient Dose Escalation](#) have been met. Additional intra-patient dose escalations will also be permitted after a minimal interval of 60 days. No crossover is allowed, however, between patients assigned to monotherapy PF-06863135 and the different combination regimens.

Following the determinations of the RP2D of monotherapy and combinations with lenalidomide or pomalidomide in Part 1, the respective expansion cohorts in Part 2 will commence. In addition, if the combination with dexamethasone in Part 1E is well tolerated as guided by mTPI, Part 2E may be initiated.

Part 2 dose expansion phase will be divided into 4 cohorts as follows: Part 2A (PF-06863135 as monotherapy), Part 2C (PF-06863135 in combination with lenalidomide), Part 2D (PF-06863135 in combination with pomalidomide) and Part 2E (PF-06863135 in

PF-06863135

C1071001

Final Protocol Amendment 9, 28 March 2023

combination with dexamethasone) which will evaluate safety and anti-myeloma activity of PF-06863135 at RP2Ds determined in Part 1.

Approximately 120 patients had been planned to enroll into Parts 1/1.1, 1C, 1D, 1E with approximately 80 patients planned to enroll into Part 2. Parts 1C, 1D and 1E were planned to enroll approximately 9-16 patients with Parts 2A, 2C, 2D and 2E planned to enroll approximately 20 patients each.

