The clinical development program for PF-06863135 has been expanded with dedicated studies that will further investigate both monotherapy and combination therapy. Therefore, the Sponsor has determined that enrollment in study C1071001 has been completed.

Study Objectives and Endpoints

Part 1 IV and SC monotherapy Dose Escalation, Part 1.1 Priming and Maintenance Dose Escalation and Parts 1C, 1D and 1E Combination Dose Escalation/Finding

| Primary Objectives: | Primary Endpoints: |
|---|--|
| 
 To assess safety and tolerability at increasing dose levels of PF-06863135 as monotherapy and in combination with lenalidomide, pomalidomide, or dexamethasone in successive cohorts of patients with multiple myeloma in order to estimate the Maximum Tolerated Dose (MTD) or Maximum Administered Dose (MAD) and select the Recommended Phase 2 Dose (RP2D). | 
 Number of DLTs following treatment with escalating doses of PF-06863135 as monotherapy and in combination with lenalidomide, pomalidomide, or dexamethasone. |
| Secondary Objectives: | Secondary Endpoints: |
| 
 To evaluate the overall safety profile. | 
 Adverse Events as characterized by type, frequency, severity as graded by National Cancer Institute Common Terminology Criteria for Adverse Events (NCI CTCAE) version 4.03, timing, seriousness, and relationship to PF-06863135 as monotherapy and in combination with lenalidomide, pomalidomide, or dexamethasone. The severity of cytokine release syndrome (CRS) will be assessed according to the grading described by Lee et al. (2014 and 2019,^{2,3} See Appendix 5); Laboratory abnormalities as characterized by type, frequency, severity (as graded by NCI CTCAE version 4.03), and timing. |
| 
 To evaluate anti-myeloma activity of PF-06863135 as monotherapy and in combination with lenalidomide, pomalidomide, or dexamethasone. | 
 Objective response rate (ORR) using the international myeloma working group (IMWG) response criteria for multiple myeloma^{4,5} (see Appendix 2); Time to event endpoints: time to response (TTR), complete response rate (CRR), duration of response (DOR), duration of complete |

PF-06863135

C1071001

Final Protocol Amendment 9, 28 March 2023

| | |
|--|---|

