1.2.3.1. Safety

The safety, efficacy, and PK of elranatamab were initially evaluated in Phase 1 study (C1071001) as monotherapy (IV and SC) or in combination with lenalidomide or pomalidomide.

As of the 22 June 2022 data cutoff date, 101 participants have been enrolled in the study as follows: 23 in Part 1 IV dose escalation, 30 in Part 1 SC dose escalation, 20 in Part 1.1 SC priming dose cohorts, 15 in Part 2A: SC dose dose expansion, 4 in Part 1C: elranatamab + lenalidomide and 9 in Part 1D: elranatamab + pomalidomide. In Part 1.1, to mitigate the risk of CRS and ICANS, participants received a priming dose of 600 µg/kg elranatamab (equivalent to 44 mg) on Day 1 prior to the first full dose of 1000 µg/kg (equivalent to 76 mg) on Day 8. In Part 2A, in addition to the priming dose of elranatamab, participants received pre-medication with dexamethasone, acetaminophen and diphenhydramine prior to the first 2 doses, priming dose and first full dose respectively.

Based on the data from this study, 76 mg QW administered SC was selected as the RP2D of elranatamab for future studies. This section will focus on safety data from participants who received elranatamab monotherapy at the full 1000 µg/kg or 76 mg [QW or Q2W] dosing regimen (N=41) regardless of priming dose or premedication.

In the 41 participants who received elranatamab monotherapy at the full 1000 µg/kg or 76 mg [QW or Q2W] dosing regimen, the most common all causality TEAEs (frequency $\geq 20\%$) were CRS (87.8%), neutropenia (78.0%), anemia (63.4%), ISR (56.1%), thrombocytopenia and fatigue (each 48.8%), diarrhea, hypophosphatemia and lymphopenia (each 39.0%), decreased appetite and dry skin (each 36.6%), back pain (34.1%), nausea and hypomagnesaemia (each 31.7%), AST increased and leukopenia (each 26.8%), ALT increased, fall, hypokalemia, pyrexia, vomiting, pain in extremity and weight decreased (each 24.4%), arthralgia, cough, dyspnoea, headache and pneumonia (each 22.0%).

For additional information, refer to the single reference safety document (SRSD), which for this study is the Investigator's Brochure.

PF-06863135
C1071001
Final Protocol Amendment 9, 28 March 2023

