9.3. Sample Size Determination

Due to the dynamic nature of the Bayesian allocation procedure, the sample size of the mTPI approach cannot be determined in advance. It is estimated approximately 100 DLT evaluable patients may be enrolled in the dose escalation stage in order to have a reliable and accurate estimate of the MTD/MAD and RP2D. At least 6 and up to 16 patients should be enrolled at a dose level that is predicted to be the MTD/MAD as per the mTPI method. However, additional cohorts below MTD/MAD may also be considered for enrollment up to approximately 6-12 patients for the purpose of confirming the RP2D.

It is anticipated that Parts 1C, 1D and 1E will each have approximately 9-16 patients enrolled. However, the total number of patients will depend on the number of dose levels needed to determine the MTD/MAD for each combination and number of patients evaluable for DLT at each cohort.

Subsequent patients will enter an expansion component, Part 2, aimed at evaluating safety and anti-myeloma activity of PF-06863135 at the RP2D in monotherapy (Part 2A) and in combination with lenalidomide, pomalidomide, or dexamethasone (Parts 2C, 2D and 2E, correspondingly). Approximately 20 patients are expected to be enrolled into each of Parts 2A, 2C, 2D and 2E, but enrollment of patients may be discontinued earlier if minimal or no anti-tumor activity is observed.

Cohort sample size is determined as follows.

Part 2A - monotherapy: Assuming a non-informative prior (ie, Jeffrey's prior) if 12 out of 20 participants have tumor response, this would predict a posterior probability (Beta Binomial) equal to 0.814 that true response rate is not inferior to target response rate of 50% and a posterior probability equal to 0.003 that true response rate is inferior to benchmark rate of 30%.

Parts 2C, 2D, and 2E – combination with lenalidomide, pomalidomide, and dexamethasone respectively: Assuming a non-informative prior (ie, Jeffrey's prior) if 14 out of 20 participants have tumor response, this would predict a posterior probability (Beta Binomial) equal to 0.818 that true response rate is not inferior to the target response rate of 60% and a posterior probability equal to 0.0001 that true response rate is inferior to benchmark rate of 30%.

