2.1. Study Design

This is a Phase 1 open-label, multi-dose, multi-center, dose escalation, safety, pharmacokinetic (PK) and pharmacodynamic study of PF-06863135 as monotherapy and in combination with lenalidomide, pomalidomide or dexamethasone in adult patients with advanced MM who have relapsed from or are refractory to standard therapy. This study will be divided into dose escalation/finding part (Part 1) and dose expansion part (Part 2). Part 1 dose escalation/finding (with either monotherapy or combination therapies) in order to determine the recommended Phase 2 dose (RP2D) is further divided into:

- *Part 1 intravenous (IV) monotherapy and Part 1 subcutaneous (SC) monotherapy cohorts as well as Part 1.1 priming and maintenance cohorts.*
- *Part 1C lenalidomide combination, Part 1D pomalidomide combination and Part 1E dexamethasone combination cohorts.*

Part 2 dose expansion phase will be divided into 4 cohorts as follows:

- Part 2A (PF-06863135 as monotherapy).
- Part 2C (PF-06863135 in combination with lenalidomide).
- Part 2D (PF-06863135 in combination with pomalidomide).
- Part 2E (PF-06863135 in combination with dexamethasone).

Approximately 120 patients are expected to be enrolled into Parts 1/1.1, 1C, 1D, 1E and approximately 80 patients are expected to enroll into Part 2. Parts 1C, 1D and 1E will enroll approximately 9-16 patients into each safety cohort. Actual number of patients enrolled will depend on the combination tolerability with lenalidomide, pomalidomide and the number of dose levels that are required to select the combination RP2Ds. Patients from the combination cohorts of Parts 1C, 1D, 1E treated at the dose levels selected for Part 2 may be counted towards the sample size of the corresponding cohorts of Part 2. Parts 2A, 2C, 2D and 2E will enroll approximately 20 patients each.

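### Enrollment closed with 15 patients in Part 2A and none listed in Parts 2C, 2D or 2E, but Protocol Section 9.3 and SAP Section 2.1 still give about 20 per Part 2 cohort

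*Protocol*

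**What the plan says.** The Protocol Summary and Section 3.1 both state that "the Sponsor has determined that enrollment in study C1071001 has been completed", because development has moved to dedicated studies. The same passages put the cohort sizes in the past tense, with "Parts 2A, 2C, 2D and 2E planned to enroll approximately 20 patients each".

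Section 1.2.3.1 gives the count: "As of the 22 June 2022 data cutoff date, 101 participants have been enrolled in the study". The breakdown is 23 in Part 1 IV, 30 in Part 1 SC, 20 in Part 1.1, and then "15 in Part 2A: SC dose dose expansion, 4 in Part 1C: elranatamab + lenalidomide and 9 in Part 1D: elranatamab + pomalidomide". Parts 1E, 2C, 2D and 2E do not appear.

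Section 9.3 was not brought into line. It still reads "Approximately 20 patients are expected to be enrolled into each of Parts 2A, 2C, 2D and 2E", and it justifies the Part 2A size as follows: "if 12 out of 20 participants have tumor response, this would predict a posterior probability (Beta Binomial) equal to 0.814" that the true rate is at least 50%, with 0.003 that it is below 30%. For Parts 2C, 2D and 2E it uses 14/20, with 0.818 against a 60% target and 0.0001 below 30%.

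SAP Section 2.1, written to the June 2021 amendment that recorded the closure, says that "approximately 80 patients are expected to enroll into Part 2", at about 20 per cohort.

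In both documents, response rate and duration of response remain the Part 2 primary endpoints, for monotherapy and for all three combinations.

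**The concern.** One version of the protocol says both that enrollment is over and that about 20 patients are still expected in each of four cohorts, of which only one has any listed patients. The section left unrevised is the one that holds the statistical justification. Section 9.3 is also the only place that gives target rates (50% and 60%) and a benchmark (30%) for the Part 2 response rate. A reader who turns to it to judge how much Part 2 can show gets a size and a certainty that belong to another trial. The gap is moderate for Part 2A and complete for the combinations. Neither document says that the combination part of the Part 2 primary objective cannot be met as planned.

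**Working it through.** **Inputs.** Planned size is 20 per cohort (Protocol 9.3, SAP 2.1). Achieved sizes come from Protocol 1.2.3.1. The prior is Jeffreys, Beta(0.5, 0.5) (Protocol 9.3).

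**Step 1: are the counts complete and final?** 23 + 30 + 20 + 15 + 4 + 9 = 101, so the listed parts use up the total and nobody is left for Parts 1E, 2C, 2D or 2E. The amendment history dates the closure statement to Amendment 8 (6 June 2021), a year before the 22 June 2022 cutoff, so the counts should not grow.

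**Step 2: planned against listed.** Part 2A: 15 of 20. Parts 2C, 2D and 2E: 0 of 3 × 20 = 60. Part 2 as a whole: 15 of 80.

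**Step 3: reproduce Section 9.3.** With x responders in n patients the posterior is Beta(x + 0.5, n − x + 0.5).

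| Outcome | Posterior | P(rate ≥ target) | P(rate < 30%) | Protocol states |
|---|---|---|---|---|
| 12/20, target 50% | Beta(12.5, 8.5) | 0.8142 | 0.0026 | 0.814; 0.003 |
| 14/20, target 60% | Beta(14.5, 6.5) | 0.8184 | 0.00011 | 0.818; 0.0001 |

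All four stated values are right. A flat Beta(1, 1) prior would give 0.808 and 0.800 against the targets, so the Jeffreys prior was the one used.

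**Step 4: Part 2A at the achieved size.** The same 60% rate at n = 15 is 9/15.

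| Outcome, target 50% | P(rate ≥ 50%) | P(rate < 30%) |
|---|---|---|
| 8/15 | 0.601 | 0.028 |
| 9/15 | 0.780 | 0.0077 |
| 10/15 | 0.902 | 0.0016 |

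At 60% the first probability falls by 0.814 − 0.780 = 0.034. The second rises about threefold (0.0077 / 0.0026).

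SAP 8.1.3 names the Wilson interval for binary endpoints. With z = 1.96 it is (x + z²/2 ± z√(np(1 − p) + z²/4)) / (n + z²):

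- 12/20: (13.92 ± 1.96 × 2.400) / 23.84 = 38.7% to 78.1%, width 39.5 points.
- 9/15: (10.92 ± 1.96 × 2.136) / 18.84 = 35.7% to 80.2%, width 44.4 points.

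**Step 5: the combinations.** Protocol 3.1.2 lets Part 1C and 1D patients treated at the dose selected for Part 2 count toward the matching cohort, and SAP 2.1 adds Part 1E. The ceilings are therefore 4 for Part 2C, 9 for Part 2D and 0 for Part 2E. Fourteen responders are impossible in any of them. For scale, against the 60% target, 3/4 would give 0.717 and 0.030, and 6/9 would give 0.650 and 0.011.

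**The case against.** The case for leaving the text alone has real content:

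- **The arithmetic is correct.** All four posterior probabilities reproduce. A reader might infer a calculation error; there is none.
- **The figures are conditional illustrations.** They say what would follow if 12 of 20, or 14 of 20, responded. A reader might infer a success criterion that the trial has failed, but no section makes either count a rule. Ten or more responders among 15 would exceed the stated 0.814.
- **The SAP does not depend on 20.** It repeats the sizes but holds no posterior probabilities for response. It summarizes efficacy without formal testing, and its response rate and interval follow the actual number treated. A reader might infer that the report will overstate its precision; the analysis plan gives no ground for that. Protocol 1.2.3.2 already reports the response rate on its actual 41 patients.
- **Much is disclosed elsewhere.** The Protocol Summary and Section 3.1 use the past tense, Section 1.2.3.1 gives the counts, sizes are always approximate, and Section 3.1.2 lets the sponsor adjust them.

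All four points stand, and they limit the finding. They do not remove it. An approximate 20 does not cover zero. Section 9.3 allows a cohort to stop early only for little or no activity, which is not the reason given for closing. Borrowing from Part 1 does not restore 20 in any combination cohort. The disclosures make the mismatch visible, but Section 9.3 and SAP 2.1 still say otherwise.

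**Conclusion.** The point holds as an outdated sample-size statement that contradicts the rest of the protocol. For Part 2A the effect is modest: at a 60% response rate, 0.780 in place of 0.814, 0.008 in place of 0.003, and an interval about 5 points wider. For Parts 2C, 2D and 2E it is total at the planned size: 0 of 60 patients listed, and at most 4, 9 and 0 available by borrowing.

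This rests on two assumptions: that the breakdown in Section 1.2.3.1 is complete, which its sum supports, and that nobody enrolled after the cutoff, which the earlier closure supports. How many Part 1C and 1D patients were treated at a dose selected for Part 2 is not stated, so 4 and 9 are upper limits. Part 2A responses are not reported separately, so 9/15 is an illustration and not a result.

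The documents do not support going further and saying that a criterion was missed or that a planned analysis is invalid.

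**What to change.** In Protocol 9.3 and SAP 2.1:

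1. Mark 20 per cohort as the planned size and give the achieved sizes: 15 in Part 2A, and no patients listed in Parts 2C, 2D or 2E.
2. Keep the 12/20 and 14/20 figures as the record of why 20 was chosen. In Section 9.3 add the Part 2A precision at 15 as an illustration (9/15: 0.780 and 0.008; Wilson interval 35.7-80.2%). Do not set a new responder threshold: response results that cover full-dose monotherapy patients are already in Section 1.2.3.2, so a threshold chosen now would be post hoc.
3. State that the Part 2 primary objective cannot be assessed at the planned size for the combinations. Say whether any Part 1C or 1D patients at the selected dose are counted toward Parts 2C or 2D under the existing rule, and how many, and that Part 2E has no listed patients.

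The cost is wording only. No patients, data or planned analyses change. If the documents are not reissued, the same statements belong in the clinical study report, where the SAP already sends deviations from the plan.
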